### 7.3 Exclusion Criteria

Subjects who meet any of the following exclusion criteria will not qualify for study participation:

1. Anemia due to a cause other than CKD or presence of active bleeding or recent blood loss
2. Sickle cell disease, myelodysplastic syndromes, bone marrow fibrosis, hematologic malignancy, myeloma, hemolytic anemia, thalassemia, or pure red cell aplasia
3. RBC transfusion within 4 weeks prior to or during screening
4. Intravenous iron within 4 weeks prior to or during screening

5. Any ESA use within 6 weeks prior to or during screening (eg, recombinant human erythropoietin, darbepoetin alfa, or methoxy polyethylene glycol-epoetin beta)
6. Aspartate aminotransferase (AST)/serum glutamic oxaloacetic transaminase (SGOT), alanine aminotransferase (ALT)/serum glutamic pyruvic transaminase (SGPT), or total bilirubin  $>2.0 \times$  upper limit of normal during screening. A history of Gilbert's syndrome is not an exclusion criterion.
7. Uncontrolled hypertension (confirmed diastolic blood pressure  $>110$  mm Hg or systolic blood pressure  $>180$  mm Hg) during screening
8. Body mass index (BMI)  $>42.0 \text{ kg/m}^2$
9. Severe heart failure during screening (New York Heart Association Class III or IV)
10. History of untreated proliferative diabetic retinopathy, diabetic macular edema, age-related macular degeneration, central retinal vein occlusion, active retinal hemorrhage, or ongoing ocular treatment with laser photocoagulation or anti-VEGF therapies
11. Acute coronary syndrome (hospitalization for unstable angina or myocardial infarction), surgical or percutaneous intervention for coronary, cerebrovascular, or peripheral artery disease (aortic or lower extremity), surgical or percutaneous valvular replacement or repair, sustained ventricular tachycardia, hospitalization for heart failure, or stroke within 12 weeks prior to or during screening
12. History of active malignancy within 2 years prior to or during screening, except for treated basal cell carcinoma of skin, curatively resected squamous cell carcinoma of skin, cervical carcinoma in situ, or resected benign colonic polyps
13. History of deep vein thrombosis (DVT) or pulmonary embolism (PE) requiring active treatment within 8 weeks prior to or during screening
14. History of hemosiderosis or hemochromatosis
15. History of prior organ transplantation or scheduled organ transplant (subjects on kidney transplant wait-list are not excluded), or prior hematopoietic stem cell or bone marrow transplant (corneal transplants and stem cell therapy for knee arthritis are not excluded)
16. Use of an investigational medication or participation in an investigational study within 30 days or 5 half-lives of the investigational medication (whichever is longer), prior to screening
17. Previous participation in a study with a hypoxia-inducible factor prolyl-hydroxylase inhibitor, other than vadadustat, within 90 days prior to screening
18. Hypersensitivity to vadadustat, or to any of its excipients

19. Females who are pregnant or breast-feeding
20. Females of childbearing potential who are unable or unwilling to use an acceptable method of contraception
21. Non-vasectomized males who are unable or unwilling to use an acceptable method of contraception
22. Any other reason that in the opinion of the investigator would make the subject not suitable for participation in the study

## **7.4 Retesting and Rescreening**

### **7.4.1 Retesting**

All screening laboratory tests, including any repeat measurements, must be performed within the screening window.

The screening period can last up to 4 weeks long, with a minimum of 4 days between the last qualifying repeat measurement and the baseline visit (Day 1), ie, the screening period window is from Day -28 to Day -4.

Subjects who initially fail to qualify for the study based on laboratory test results may have their laboratory value retested once within the screening period, at the investigator's discretion.

Retesting within the screening period does not constitute rescreening; however, if retesting falls outside of the screening period, it should be considered a rescreen.

### **7.4.2 Rescreening**

Subjects who fail to meet the qualifying criteria for Hb or eGFR during screening may be considered for rescreening at the discretion of the investigator, if it is felt that the subject's status has changed and that the subject may now qualify for the study. Additionally, subjects who fail to qualify for the study based on low ferritin, TSAT, folate, or B12 values may be considered for rescreening after receiving replacement therapy.

If intravenous (IV) iron is used to replete iron stores, the last dose of IV iron must be administered at least 4 weeks prior to rescreening.

Screening is limited to 3 attempts (during the initial screening and 2 additional rescreening attempts). Subjects who fail to qualify for the study at the initial screening visit will receive a new subject number for each rescreening attempt. If rescreened, the subject will also sign a new informed consent form and will repeat all screening procedures for each rescreening attempt.

## **7.5 Study Completion, Study Termination, and Individual Study Site Termination**

### **7.5.1 Study Completion**

The study will be considered completed after all enrolled subjects have completed study participation, and the adverse event (AE) reporting period has been completed for each enrolled subject (see [Section 10.3.1](#) for information regarding the AE reporting period).

### 7.5.2 Study Termination

The entire study may be suspended or terminated by the sponsor for safety or other unanticipated reasons or upon request of regulatory agencies. Criteria for premature study termination or suspension are detailed in [Section 14.1](#).

### 7.5.3 Individual Study Site Termination

Study participation may be suspended or terminated at an individual investigational site for various reasons. Criteria and procedures for premature termination or suspension of an investigational site are detailed in [Section 14.2](#) and [Section 14.3](#).

## 7.6 Subject Completion and Individual Subject Discontinuation

### 7.6.1 Subject Completion

A subject randomized to receive placebo will be considered as having completed the study after completing participation in the Week 10 (unblinding) visit.

A subject randomized to receive vadadustat will be considered as having completed the study after completing participation in the Week 18 visit (end of the 2-week safety follow-up period).

Note that for subjects who discontinue study drug due to an excess Hb response during the primary efficacy period, Hb levels will be monitored weekly via lab evaluation until the subject no longer exhibits an excess Hb response.

See [Section 10.3.6](#) for information regarding follow-up of unresolved events.

### 7.6.2 Conditions and Documentation of Individual Subject Study Drug Discontinuation

Subjects will discontinue study medication for any of the following conditions:

- Completion of the protocol-defined dosing period (see [Appendix A](#))
- Meets discontinuation criteria related to excess Hb response during the primary efficacy period (defined in [Section 8.2.4](#))
- Major toxicity considered to be related to study medication
- Worsening of anemia requiring ESA rescue or blood transfusion
- Administrative reasons, such as, subject non-compliance or a major protocol violation
- Upon request of the sponsor or regulatory agency
- If, in the opinion of the investigator, it is medically necessary, or if it is the wish of the subject
- Study termination (see [Section 14](#))

The investigator must document the primary reason for discontinuation in the appropriate case report form (CRF).

### 7.6.3 Individual Subject Discontinuation during the Primary Efficacy Period or Blinded Dose Adjustment and Data Cleaning Period

Subjects discontinuing study medication or withdrawing early from the study during the blinded periods should undergo the Week 10 (EOT for blinded period) clinical and laboratory assessments within 1 day of stopping study medication, if possible. Such subjects should also complete the 2-week safety follow-up period (see Appendix A). For subjects who discontinue

study medication, the investigator should resume standard of care treatment, as deemed appropriate.

If a subject does not return for a scheduled visit, every effort should be made to contact the subject.

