## 11 DATA ANALYSIS

### 11.1 Primary Endpoint and Sample Size Determination

The primary objective of this study is to quantify the dose-response relationship between oral vadadustat once daily dosing for 6 weeks and change in Hb in Japanese subjects with NDD-CKD in order to define the starting dose for use in Phase 3 clinical studies in Japan.

Change in Hb is defined as the Hb measured at the EOT visit minus the mean pre-treatment Hb. Pre-treatment Hb is defined as the average of 2 Hb values obtained prior to treatment based on the qualifying screening Hb value and the Hb value at the baseline visit. Linear regression analysis will be used to calculate the relationship between vadadustat dose and change in Hb.

The target enrollment will be approximately 48 subjects for the study with 12 subjects enrolled in each of the 4 treatment groups.

Based on the results from Study AKB-6548-CI-0005 that was conducted in the United States and evaluated vadadustat in patients with anemia secondary to NDD CKD, it is reasonable to assume that the expected mean Hb changes from baseline to Week 6 will be 0, 0.5, 0.7, and 1.2 g/dL for the placebo, 150 mg, 300 mg, and 600 mg vadadustat dose groups, respectively, with a common standard deviation of 0.68 g/dL among the 4 treatment groups. With these assumptions, the study will have >85% power to detect a non-zero slope in a dose-response relationship using linear regression analysis and  $\alpha=0.05$ , based on simulation of 10,000 repetitions using SAS® software, Version Number 9.4.

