	components of the complete blood count [CBC] other than the ones noted above, and vascular endothelial growth factor [VEGF])
Dosage and Regimen	
Study drug will be administered on an outpatient basis. Subjects should take the study medication with water or other oral beverage and should be instructed to swallow the intact tablet(s). Subjects may take the study medication with or without food.
 
Note: Hb will be assessed at the central laboratory and also monitored using point-of-care HemoCue®. Note that the point-of-care HemoCue Hb value will be used to determine if the dose of study medication will be adjusted or discontinued.
 
Primary efficacy period (Day 1 to Week 6)
 
Using a central randomization system, subjects will be randomized at a 1:1:1 ratio to receive 1 tablet (150 mg vadadustat or placebo), 2 tablets (300 mg vadadustat or placebo), or 4 tablets (600 mg vadadustat or placebo) of study drug. Within each tablet-count group, subjects will be randomized 3:1 to receive vadadustat or placebo as shown below.
 <pre>graph LR     A[1 tablet (n=16)] --> B[Vadadustat 150 mg (n=12); 1 x 150 mg tablet once daily]     A --> C[Placebo (n=4); 1 tablet once daily]     A --- D[2 tablets (n=16)]     D --> E[Vadadustat 300 mg (n=12); 2 x 150 mg tablets once daily]     D --> F[Placebo (n=4); 2 tablets once daily]     D --- G[4 tablets (n=16)]     G --> H[Vadadustat 600 mg (n=12); 4 x 150 mg tablets once daily]     G --> I[Placebo (n=4); 4 tablets once daily]</pre> 
The primary efficacy period includes a fixed-dose treatment to establish a dose-response relationship. However, if Hb level increases too rapidly or if the Hb levels exceed the desired range, the blinded study drug dose will be decreased or discontinued as presented below.
 

Subjects who meet the following criteria for excess Hb response will undergo a dose reduction by 1 tablet:

Hb increase >1 g/dL within any 2-week period, OR

Hb increase >2 g/dL within any 4-week period, OR

Hb level >13 g/dL

Subjects who meet the following criteria will discontinue study drug:

Excess Hb response as defined by any of the aforementioned criteria, AND

Current dose 1 tablet OR subject had previously decreased study drug dose due to excess Hb response

 
Blinded dose adjustment and data cleaning period (Week 7 to 10)
 
During this period, data from screening through the Week 6 visit will be cleaned and locked in preparation for the Week 10 unblinding visit. Blinded study drug dosage will be adjusted to achieve a target Hb 10-12 g/dL. Starting at the Week 6 visit,

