Rescue Therapy Guidelines	
The following rescue therapy guidelines are provided to ensure the safety of study subjects and to standardize the use of rescue in the study.
 

• ESA rescue: ESA rescue therapy may be considered based on the investigator's judgment, if a subject:

- Experiences a clinically significant worsening of anemia or symptoms of anemia, and

- Exhibits Hb level <9.0 g/dL

• RBC transfusion: Investigators should use their local institution's transfusion guidelines when determining whether to transfuse a study subject.

 
Subjects who initiate rescue therapy will be required to stop study drug treatment and will be discontinued from the study.

Oral Iron Supplementation	
Subjects who are taking oral iron supplementation at baseline should continue their oral iron at the same dose throughout their study participation. Changes to oral iron supplementation dose will be considered protocol deviations but will not be considered a reason for subject discontinuation.
 
Subjects who are not taking oral iron supplementation at baseline should not start

	
oral iron during their study participation.
 
Important: Because of the potential for oral iron to reduce the bioavailability of vadadustat, study drug (vadadustat or placebo) should not be administered concurrently with any oral iron supplement. Any oral iron supplements (including multivitamins containing iron) should be taken at least 2 hours before or 2 hours after the dose of study drug.

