Statistical Considerations	
The primary analysis will use a linear regression analysis to quantify the association between vadadustat dose and mean change in Hb (ie, to assess the vadadustat dose-response relationship). Comparison of each vadadustat dose group versus baseline will be performed. All tests of significance will be performed using a 0.05 two-sided significance level.
 
The target enrollment will be approximately 48 subjects for the study with 12 subjects enrolled in each of the 4 treatment groups. Based on the results from Study AKB-6548-CI-0005 that was conducted in the United States and evaluated vadadustat in patients with anemia secondary to NDD-CKD, the expected mean Hb changes from baseline to Week 6 will be 0, 0.5, 0.7, and 1.2 g/dL for the placebo, 150 mg, 300 mg, and 600 mg vadadustat dose groups, respectively, with a common standard deviation of 0.68 g/dL among the 4 treatment groups. With these assumptions, the study will have >85% power to detect a non-zero slope in a dose-response relationship using linear regression analysis and <math>\alpha=0.05</math>, based on simulation of 10,000 repetitions using SAS® software, Version Number 9.4.

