## 6.3 Rationale for Study Design

The study design of this randomized, double-blind, placebo-controlled, dose-finding study in Japanese subjects with anemia secondary to NDD-CKD is modeled on a previously completed dose-finding study in Caucasian subjects with anemia secondary to NDD-CKD (Study AKB-6548-CI-0005).

A treatment duration of 6 weeks will be adequate to demonstrate the dose-response relationship of vadadustat with change in Hb, as 6 weeks of treatment with vadadustat in

Study AKB-6548-CI-0005 was adequate to establish a statistically significant dose-response relationship (as shown in Figure 4). An additional 10-week maintenance period will be conducted to evaluate the effect of dose adjustments and demonstrate the maintenance effect on Hb.

**Figure 4: Absolute Change in Hemoglobin ( $\pm$  Standard Error of Mean, g/dL) at Week 6 Compared to Baseline (Study AKB-6548-CI-0005)**

Note: 25% of the subjects in the 630 mg vadadustat treatment group and 10% of subjects in the 500 mg vadadustat treatment group had their doses reduced by Week 4.

Note: Two tailed paired t-test of hemoglobin: Baseline versus Week 6,  $p < 0.01$

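### Stopping for excess Hb depends on Hb and on tablet count, and the protocol does not settle which Hb is then the primary value, which matters mainly in the 150 mg group

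*Protocol*

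**What the plan says.** The protocol file holds successive versions, and the latest breaks off in Section 8.1.4. Sections 9 to 11 and Appendix A are cited from the version before it.

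- **Stopping.** A first excess Hb response lowers the dose by one tablet. Study drug stops (Synopsis, Dosage and Regimen) on an excess response plus this condition: "Current dose 1 tablet OR subject had previously decreased study drug dose due to excess Hb response". A 1-tablet subject therefore stops at the first event, a 2- or 4-tablet subject at the second.
- **After stopping.** Section 7.6.3: such subjects "should undergo the Week 10 (EOT for blinded period) clinical and laboratory assessments within 1 day of stopping study medication", if possible, followed by the 2-week safety period. After an excess-Hb stop, laboratory Hb is also taken weekly, but only until the excess has resolved (Section 7.6.1).
- **Rescue.** "Subjects who initiate rescue therapy will be required to stop study drug treatment and will be discontinued from the study" (Synopsis).
- **Primary value.** Sections 5.1 and 11.5 use the change from pre-treatment to Week 6. Section 11.1 uses Hb at the EOT visit minus the pre-treatment mean. Appendix A attaches the EOT label to Weeks 10 and 16, never to Week 6.
- **Populations.** The MITT population for Hb needs one post-baseline value. The per-protocol population needs study completion and data through Week 6 (Section 11.2.2).

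**The concern.** The probability of having a Week 6 Hb depends on the Hb response and on the tablet group. A strong early responder at 150 mg is removed at once, while an equally strong responder at 300 or 600 mg continues on a reduced dose. A regression on completers then understates the 150 mg response, in a trial meant to choose a starting dose.

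The EOT wording does not cure this. It replaces a missing value with one selected because it was high, and taken up to five weeks before Day 43. Read literally for completers, it also points to Week 10, after four weeks of dose adjustment. The one sensitivity population named, per protocol, leaves out the same subjects.

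**Working it through.** **1. The plan's power.** Inputs: means "0, 0.5, 0.7, and 1.2 g/dL for the placebo, 150 mg, 300 mg, and 600 mg vadadustat dose groups, respectively", "standard deviation of 0.68 g/dL among the 4 treatment groups", 12 per group, and "All tests of significance will be performed using a 0.05 two-sided significance level".

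- Mean dose 262.5 mg; Sxx = 12 × (262.5² + 112.5² + 37.5² + 337.5²) = 2,362,500.
- Sxy = 12 × (157.5 + 11.25 + 3.75 + 202.5) = 4,500; slope = 4,500 / 2,362,500 = 0.001905 g/dL per mg.
- SE = 0.68 / √2,362,500 = 0.000442; non-centrality = 4.305 on 46 df; power 98.8%.

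This satisfies the statement in Section 11.1: "With these assumptions, the study will have >85% power to detect a non-zero slope in a dose-response relationship using linear regression analysis". Losing 3 of 12 at 150 mg alone leaves 98.8%; losing 3 of 12 in every group leaves about 95%. The issue is bias at one dose, not power.

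**2. Which stoppers have an Hb near Day 43 ± 3 (Days 40 to 46)?**

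| Stop at | EOT visit by | Follow-up CBC about | In Week 6 window? |
|---|---|---|---|
| Week 1 (Day 8) | Day 9 | Day 22–23 | No |
| Week 2 (Day 15) | Day 16 | Day 29–30 | No |
| Week 4 (Day 29) | Day 30 | Day 43–44 | Yes, about 2 weeks off drug |

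Weekly monitoring may happen to reach Day 43 but is not required to.

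**3. How many stop, and what happens to the means.** The simulation uses a linear rise to the planning means, with subject-slope variance chosen so that the Week 6 change has SD 0.68. With within-subject SD s and a two-value baseline, the variance of the true change is 0.68² − 1.5s²; for s = 0.3 this is 0.4624 − 0.135 = 0.327. The rules of more than 1 g/dL in 2 weeks and more than 2 g/dL in 4 weeks are applied at Weeks 1, 2 and 4. The documents do not give s, so it is an assumption, shown over a range.

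| s (g/dL) | Stopped before Week 6: 150 / 300 / 600 mg | 150 mg completer mean (true 0.50) | 150 mg mean using EOT value |
|---|---|---|---|
| 0.2 | 2% / 0.1% / 0.7% | 0.48 | 0.49 |
| 0.3 | 10% / 1% / 2% | 0.44 | 0.49 |
| 0.4 | 22% / 3% / 6% | 0.42 | 0.53 |

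At 150 mg that is 12 × 0.02 = 0.2 to 12 × 0.22 = 2.6 subjects. At s = 0.4 about 15% of the 1-tablet placebo subjects stop as well. If HemoCue, which drives the rule, adds its own error of up to 0.5 g/dL, the ranges widen to 2–47%, 0.1–8% and 0.6–12.5%. In every scenario the 1-tablet group has the most stops. Between 55 and 68% of the 150 mg stops fall at Weeks 1 and 2, where step 2 shows no required Hb near Day 43.

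**4. Loose calibration.** Section 6.3 reports that "25% of the subjects in the 630 mg vadadustat treatment group" had doses reduced by Week 4 in the earlier study. The model gives 23% reduced at 600 mg for s = 0.3 and about 37% for s = 0.4, so s = 0.3 fits better. The earlier study's reduction rules are not given, so this is only a rough check.

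**5. Remedies compared at 150 mg (true 0.50).** Using Day 43 Hb from stoppers as primary, with an assumed fall of 0.1 g/dL per week off drug, gives 0.42 (s = 0.3) and 0.33 (s = 0.4), further away than completers alone. A repeated-measures model on on-treatment laboratory Hb at Weeks 1, 2, 4 and 6 returns 0.50 in both cases and the planned mean in the other arms, because stopping depends on Hb that the model contains. This requires the HemoCue reading to be the laboratory Hb plus independent error. If device and laboratory values varied independently of each other, only part of the shift would be removed.

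**The case against.** - **Section 11.1 gives early stoppers a value.** This stands. A reader might infer that they simply drop out of the primary model; the documents do not establish that. They establish two definitions that disagree. On the EOT reading the net shift at 150 mg is small in these scenarios (−0.01 to +0.03 g/dL), but only because an inflated reading and a shortened exposure happen to offset each other.
- **Stoppers do not all leave without Hb.** This also stands. Leaving the study is explicit only for rescue, weekly Hb follows an excess-Hb stop, and a Week 4 stopper has a CBC near Day 43. The gap is firm for Week 1 and Week 2 stops.
- **Missing-data handling belongs in the SAP.** Fair for the choice of model. It does not cover a contradiction over the primary value within the protocol itself.
- **The effect is small.** A shift of 0.06 g/dL is about 0.3 of the standard error of a 12-subject mean (0.68/√12 = 0.20), and the slope test is robust. This limits the weight of the point but does not remove it.
- **Rescue might be thought to strip low-Hb subjects mainly from placebo.** No rescue rate is given and rescue has no tablet-count rule, so no claim about rescue by arm is supported.

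**Conclusion.** The point holds in limited form. Stopping for excess Hb is triggered by the outcome and is stricter in the 1-tablet group. The protocol then leaves two incompatible primary values, and either one depends on the outcome for early stoppers. On the Week 6 reading the 150 mg completer mean is about 0.02 to 0.08 g/dL too low, with about 2 to 22% of that group stopping early. These sizes rest on an assumed within-subject SD of 0.2 to 0.4 g/dL, a linear rise and the planning means.

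A reader might go on to infer that the trial is underpowered or that its slope is unreliable. The figures do not support that: power stays near 99% with 3 of 12 lost at 150 mg alone. The unseen remainder of the latest version could already reconcile the two definitions.

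**What to change.** Leave the stopping and rescue rules as they are.

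1. Reconcile Section 11.1 with Sections 5.1 and 11.5, so that the primary value is the change from the pre-treatment mean to Week 6.
2. Estimate the Week 6 dose response from a repeated-measures model by randomised dose, using all on-treatment central-laboratory Hb at Weeks 1, 2, 4 and 6. Make it at least the named sensitivity analysis, since the per-protocol set excludes the subjects at issue.
3. Optionally, take a CBC at Day 43 ± 3 from subjects who stopped drug but remain in the study. Use it only in a supportive treatment-policy analysis: these values are off drug and may reflect resumed standard of care (Section 7.6.3).

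The cost is a short text change and slightly more analysis on data already collected. If item 3 is adopted, add one blood draw in a few subjects, some of whom are already having weekly Hb.
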